Length of Cook Catheter Placement and Induction of Labor

NCT04233008

Version date 2/21/18

Partners Human Research Committee Detailed Protocol

[name]
[name] (principal investigator)

Study Title: Length of foley catheter placement and induction of labor: a randomized controlled trial

Version date 2/21/18

Background and Significance

Induction of labor occurs in 24% of pregnancies in the United States (Hamilton). There are many maternal and fetal indications for induction of labor at various gestational ages of pregnancy. Induction of labor consists of initial cervical ripening followed by oxytocin. Cervical ripening helps the cervix soften, thin and dilate. There are multiple agents for cervical ripening including pharmacologic and mechanical dilation. Pharmacologic agents include prostaglandins and oxytocin. Mechanical ripening most commonly refer to a foley catheter balloon device. Mechanical methods have been associated with lower rates of cesarean section compared with oxytocin alone (Boulvain). Previous studies have compared foley catheter placement for 12 vs. 24 hours and showed 12 hours decreases time to delivery (Cromi). Recently, studies have looked at the efficacy of dual induction agents with combination of oxytocin and foley catheter with time to delivery (Levine).

The cook catheter device, a type of foley catheter used for mechanical dilation, is a silicone double balloon catheter that can be inflated to 80mL/balloon. Per device guidelines it should not be left in place for more than 12 hours. Given these instructions the balloon is most often removed at 12 hours or spontaneously when it falls out given cervical dilation during the induction process.

Currently there are no studies that evaluate the time to delivery in women with the foley catheter removed at 6 hours vs. 12 hours. Our theory is that the benefit of the foley catheter is within the first 6 hours and we will study whether there is faster time to delivery in this intervention group.

This study has potential benefits for both individuals, hospital efficiency, and healthcare costs in the future. Longer inductions are associated with higher rates of postpartum hemorrhage and infection, therefore decreasing induction length would hopefully limit these labor complications. By decreasing the length of time for induction of labor, hospital and efficiency and healthcare costs would likely improve. Patients in the future would benefit from the knowledge gained in this trial if labor inductions are shorter with only 6 hours of a foley catheter placement and labor induction protocols change as a result.

Specific Aims

The objective of our study is to compare the time to delivery in women who undergo induction of labor with foley catheter and oxytocin for six vs. twelve hours. Our

hypothesis is women who undergo an induction with foley catheter for 6 hours will have a shorter time to delivery.

Subject Selection

Our study population will include women 18-50 years of age at term (37-41 6/7 weeks) with a singleton gestation in cephalic presentation who are undergoing induction of labor. Both nulliparous and multiparous women will be included. Women will need to have a bishop score <6 or cervical dilation <2cm with intact membranes to be included, as these are the women currently being offered cervical ripening prior to labor induction. Women will be excluded if there is a contraindication to vaginal delivery. Women with history of a prior cesarean section will be excluded given their management may differ after removal of the foley catheter. Non-English speaking women will also be excluded given the length of time for induction on labor and delivery and inability to guarantee 24 hour interpreter services.

Women will be recruited from the Maternal Fetal Medicine and general Obstetrics clinics at Brigham and Women's Hospital. They will be counseled in the office by their provider when an induction of labor is discussed, based on their cervical examination.

Subject Enrollment

Women will be enrolled from clinic prior to induction of labor based on their cervical exam and need for cervical ripening. Typically, inductions are scheduled in clinic within the week prior. When a patient is being scheduled for an induction, and it is deemed that they will need cervical ripening, they are potential candidates for this trial. The process of informed consent will happen in the clinic if the patient desires to participate in the study. The study staff and other selected physicians in clinic who have agreed to help with the study will consent the patient. Once consent is obtained, the subjects will then be randomized to either 6 vs. 12 hours with foley catheter. A random number generator will be used to randomize women in blocks of 10.

If a woman is unsure about her desire to participate she will be able to go home from clinic with time to consider participation. If this is the case, she will be consented when she presents for her induction of labor by the study staff.

Often times women at term are seen in clinic and the decision is made to proceed with induction on the same day. We propose that we are able to approach these women when they present to labor and delivery for induction. They will be given at least one hour to consider participation in the trial and to ask pertinent questions.

Neither the patients nor the health care providers will be blinded to the assigned treatment group due to practical limitations.

Study Procedures

Upon presentation to labor and delivery the participant will have a foley catheter inserted digitally or by direct visualization with a speculum, as per provider preference as both methods are commonly used. The uterine component of the balloon will be inflated to maximum 60mL. The catheter will be taped to the inner thigh with gentle traction.

Below is an image of cook catheter with both uterine and vaginal balloons inflated. In this study we will only inflate the uterine balloon (the distal balloon), following current standard practice on our labor and delivery unit.

In both groups participants will be started on a hospital-based oxytocin protocol. This protocol begins with 2 milliunits/min of oxytocin, increasing by 2 milliunits every 15 minutes until regular uterine contractions occur. The maximum dose of oxytocin is considered to be 30 milliunits per our current protocol.

The foley catheter will then be removed at 6 vs. 12 hours based on randomization. At that point health care providers will manage active labor per usual practice. Pitocin will be continued after foley removal, as is standard practice and health care providers may perform amniotomy at any point during the induction process with a recommendation for amniotomy when cervix more than 4cm dilated, consistent with literature demonstrating a shorter time to delivery with earlier amniotomy (Battarbee). Labor interventions are at the discretion of the healthcare provider. The participants will have continuous fetal monitoring throughout their induction, labor and delivery. The need for operative delivery or cesarean section will be at the discretion of the healthcare provider.

Biostatistical Analysis

The main outcome will be length of time to delivery. A subject's participation will end with outcomes 4 weeks following delivery.

Secondary maternal outcomes will be measured including cesarean delivery rate, time to active labor (>5cm dilated), delivery within 12 hours, delivery within 24 hours, maternal length of stay, and indication for cesarean delivery. We will also calculate a composite maternal morbidity outcome including estimated blood loss, higher-order laceration, blood transfusion, endometritis, wound infection, venous thromboembolism, hysterectomy, ICU admission or death. These outcomes will also be stratified by parity. We will also evaluate rates of analgesia in both groups.

A composite neonatal morbidity will be calculated including culture-proven neonatal sepsis, neonatal blood transfusion, hypoxic-ischemic encephalopathy, intraventricular hemorrhage grade 3 or 4, or therapeutic hypothermia. We will also analyze NICU admission, NICU admission for greater than 48 hours, and neonatal length of stay.

In the literature, the mean time to delivery with an induction of labor is 18 hours. A four hour reduction in time to delivery is considered clinically meaningful and has been used in prior studies evaluating induction of labor (Levine). A Type I α error of 0.05

was selected. Assuming 80% power and a two-sided P value we would need 71 participants in each group for total sample size 142. However, given that some patients will undergo cesarean section during their induction of labor, we will exclude cesarean section in a sensitivity analysis. Assuming that 20% of patients will have a cesarean section, we will include 89 women in each arm, 178 women total. For statistical purposes, intent to treat analysis will be performed. Non-parametric measures will be used for statistical analysis. These models will also be adjusted for parity.

Risks and Discomforts

Women may experience discomfort with foley catheter insertion, which will be handled with pain medication in a similar way to current practices on labor and delivery.

Because the foley catheter is routinely used for cervical ripening during labor induction on labor and delivery we think that there is minimal increased risk from the study. However, by limiting the foley catheter to 6 hours, the length of time of cervical ripening is limited. Upon removal of the catheter at 6 hours the cervix may not be ripened and therefore increase the risk of prolonged induction and ultimately cesarean section. If the intervention group is associated with longer length of time to delivery it may also be associated with increased blood loss and risk of infection, which are known risks of prolonged induction. Our study, however, allows physicians to manage labor as deemed appropriate after foley removal. Thus, if cervical ripening is felt to be inadequate, alternative cervical ripening agents (such as misoprostol) could still be used in appropriate candidates. Moreover, we feel it is most likely that the 12-hour foley group (the current standard of care) will have longer labor inductions, not the 6-hour experimental group, consistent with prior studies showing that labors were longer with 24 hour foley placement rather than 12 hour placement (Cromi). Also, our clinical experience is that when foley balloons are actively managed (i.e. the patient is checked vaginally sooner than 12 hours and tension is applied to see if the foley is ready to come out) most women achieve adequate cervical dilation much sooner than the maximum of 12 hours.

Potential Benefits

Because this study is a randomized controlled trial, there is no direct benefit to individuals. Given the nature of the study we do not know if, and which treatment is better. Furthermore, the study is randomly allocated so there is an equal chance of the patient being in either treatment arm.

There are however many benefits for the healthcare system in the future. By determining the faster method for induction of labor we may find that risk of infection and blood loss are lessened. The fetus also benefits by shorter induction times by limiting the time of intrauterine stress during labor and delivery. Healthcare cost would benefit from the information gained in this study by decreasing hospital stays. Currently, the most effective method of inducing labor remains unknown.

Monitoring and Quality Assurance

The principal investigator will review the entries for each participant to ensure they are complete. We will not perform any interim analysis, as we feel there is minimal risk from the study protocol and would not stop the study early. When adverse events

occur they will be reported to the Partners' IRB within 5 days with a detailed description of the event as described in the guidelines for adverse events reporting. Serious adverse events (severe hemorrhage, maternal death, neonatal death, neonatal hypoxemic encephalopathy) will be reviewed by the head of labor and delivery and the study staff to ensure the outcome is not related to the study protocol.

References

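### The cervical examination that decides entry is not used as a covariate; adding it to the parity-adjusted models would be a low-cost gain in precision of modest and uncertain size

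*Combined protocol and SAP*

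**What the plan says.** Subject Selection sets the entry rule: "Women will need to have a bishop score <6 or cervical dilation <2cm with intact membranes to be included". The Bishop score and dilation appear there as eligibility criteria; neither is named later as a covariate or a stratification factor.

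Subject Enrollment places most consent and randomization in clinic and says of timing: "Typically, inductions are scheduled in clinic within the week prior". Other women are approached or consented on labor and delivery. Allocation is described as "A random number generator will be used to randomize women in blocks of 10", with no stratification stated. Potential Benefits confirms 1:1 allocation: "there is an equal chance of the patient being in either treatment arm".

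Biostatistical Analysis states "The main outcome will be length of time to delivery" and lists "time to active labor (>5cm dilated") among the secondary outcomes. Neither has a stated time zero. On method it says "Non-parametric measures will be used for statistical analysis", then "These models will also be adjusted for parity". No test or model is named. The secondary maternal outcomes are also to be broken down by parity.

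**The concern.** Women enter because their cervix is unfavorable, but not equally so. The two criteria are joined by *or*, so a woman at 2 cm or more still qualifies if her Bishop score is below 6. The starting state therefore varies among participants.

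It is reasonable to expect that state to predict how long induction takes. Risks and Discomforts reasons along these lines when it warns that a cervix not ripened when the catheter comes out at 6 hours could mean a prolonged induction. That remark concerns the cervix at removal, so it supports the expectation without proving it for the cervix at entry. For time to active labor the link is more direct, because that outcome is itself a dilation threshold.

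A prognostic baseline variable left out of the model stays in the residual variance. In a trial of 178 women without stated stratification, covariate adjustment is the remaining tool for removing it. Because the trial is open-label, a covariate chosen after the data are seen would look selective, so it has to be named in advance. What is at stake is precision only.

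**Working it through.** **1. The plan's own figures.** Inputs from Biostatistical Analysis: difference 4 h, two-sided alpha 0.05, power 80%, 71 per group, 20% cesarean, 89 per arm. No standard deviation is stated, so 71 cannot be reproduced from stated inputs. Solving for it:

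SD = 4 × √(71/2) / (1.960 + 0.842) = 8.51 h (normal approximation; 8.45 h by the noncentral t).

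An SD of 8.5 h returns 71 per group. The inflation step reproduces: 71 / (1 − 0.20) = 88.75, rounded up to 89.

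**2. Gain before costs.** Let r be the correlation, within parity groups, between the pre-randomization cervix and time to delivery. The documents do not give it; 0.2 to 0.4 is assumed. In a linear model the residual variance is multiplied by (1 − r²), and the confidence interval narrows by 1 − √(1 − r²).

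**3. Cost of the covariates.** Two extra covariates inflate the variance by about (N − 5)/(N − 7). At N = 178 this is 173/171 = 1.0117, or 1.2%. At N = 142 it is 137/135 = 1.0148, or 1.5%. A single covariate costs less.

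**4. Net gain at N = 178.** Variance factor f = (1 − r²) × 1.0117; narrowing = 1 − √f; equivalent extra women = 1/f − 1.

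| r | r² | Narrowing before cost | f | Net narrowing | Equivalent extra women |
|---|---|---|---|---|---|
| 0.14 | 0.02 | 1.0% | 0.991 | 0.4% | 0.9% |
| 0.2 | 0.04 | 2.0% | 0.971 | 1.4% | 3.0% |
| 0.3 | 0.09 | 4.6% | 0.921 | 4.0% | 8.6% |
| 0.4 | 0.16 | 8.3% | 0.850 | 7.8% | 17.7% |

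These ratios do not depend on the SD. Break-even is r² = 1 − 171/173 = 0.012; below that, two covariates cost more than they return.

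**5. On the power scale.** This step takes 8.5 h as the residual SD of the parity-adjusted model, a further assumption because the plan does not say what its SD represents. Power = Φ(4 / (8.5 × √f × √(2/89)) − 1.96). With 89 per arm:

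- without the cervix (f = 1): 88.1%
- r = 0.2: 89.0%
- r = 0.4: 92.6%

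The gain is about 1 to 4.5 percentage points.

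**The case against.** The strongest reply is that omitting a further prognostic covariate from a randomized comparison introduces no bias, that parity adjustment is already planned, and that the choice of covariates is partly preference. That stands, and it is why the point concerns efficiency only. Restricting entry to women who need ripening may also narrow the range of the covariate and weaken it. The size of the gain cannot be settled from the documents.

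A second reply is that the plan specifies non-parametric methods and a plain rank test takes no covariates. This limits the arithmetic: the formulas above hold for a linear model, and in a Cox model adjustment also changes the hazard ratio being estimated. It does not block the change, because the plan already commits to models adjusted for parity and so needs a method that accepts covariates.

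A reader might infer four stronger claims that the documents do not support:

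- *Both time outcomes run from the qualifying examination.* No time zero is defined, and for women randomized in clinic the examination may precede catheter insertion by up to about a week.
- *The gain is free because both values are already obtained for every woman.* Under an *or* rule either measure alone can qualify a woman, and nothing says that both are recorded.
- *The primary outcome lies on the same scale as the entry measure.* Time to delivery is in hours; only the secondary threshold of more than 5 cm shares the dilation scale.
- *A chance imbalance would shift the result by 0.5 to 1.0 h.* That figure comes from 2 × √(2/89) × r × 8.51 with r from 0.2 to 0.4. It applies a within-parity correlation to an SD not shown to be within parity, and so may overstate the shift. A two-standard-error imbalance is also roughly a 1-in-20 event that the confidence interval already allows for, so it counts the same loss of precision twice.

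**Conclusion.** The point holds as a recommended efficiency improvement. The entry rule uses the starting cervix, parity is the only named covariate, and no stratification is stated. Adding the pre-randomization cervical examination would narrow the confidence interval by about 1.5% to 8%, net of two covariates. This rests on an assumed within-parity correlation of 0.2 to 0.4 and a linear model. If the cervix explains about 2% of the variance or less, the gain is close to nil. Nothing in the documents makes the planned comparison biased or invalid without this change.

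**What to change.** In Biostatistical Analysis, change the adjustment sentence to read: *adjusted for parity and for the cervical examination (Bishop score, or dilation if the score is not available for all women) at the last examination before randomization*. Apply it to time to delivery and time to active labor, and name the covariate-capable model in which both adjustments are made. Record the chosen measure and the examination date for every woman. Use the pre-randomization value, because for women randomized in clinic any later examination would be made with the allocation known.

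Cost: one sentence, one more recorded item for some women, and one or two degrees of freedom. For women randomized in clinic the covariate may be up to about a week old at insertion, while for those enrolled on labor and delivery it may be more recent. This mixture of timings may weaken the covariate, but it does not affect validity. No additional participants are needed.

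### Women who consent in clinic are randomised there, typically up to about a week before the catheter, with no eligibility re-check on admission described; randomising just before placement would be better

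*Combined protocol and SAP*

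**What the plan says.** Subject Enrollment describes three routes into the trial.

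- **Clinic.** Consent is taken in clinic when the induction is booked: "Typically, inductions are scheduled in clinic within the week prior". Allocation comes next: "Once consent is obtained, the subjects will then be randomized to either 6 vs. 12 hours with foley catheter".
- **Undecided women.** They go home to think it over: "If this is the case, she will be consented when she presents for her induction of labor by the study staff".
- **Same-day inductions.** "Often times women at term are seen in clinic and the decision is made to proceed with induction on the same day". For these, "We propose that we are able to approach these women when they present to labor and delivery for induction".

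The second and third routes therefore leave no long gap. The first does.

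The entry criteria in Subject Selection describe the woman's state at the time of examination: "Women will need to have a bishop score <6 or cervical dilation <2cm with intact membranes to be included". In Study Procedures the next step is placement: "Upon presentation to labor and delivery the participant will have a foley catheter inserted digitally". No repeat examination or confirmation of eligibility is described in between, and there is no rule for a randomised woman who no longer qualifies.

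Biostatistical Analysis names time to delivery as the main outcome without giving its starting point. It specifies an intent-to-treat analysis with non-parametric methods, and it raises the sample size from 71 to 89 per arm for cesarean only. Subject Enrollment states that neither patients nor providers are blinded.

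**The concern.** The two arms are treated alike until 6 hours after placement. Allocating days earlier gains nothing for the comparison, and it lets in women who will never be exposed to the difference under study. Between clinic and admission a woman may go into labor, rupture her membranes, ripen enough not to need the catheter, or withdraw. As written, the plan has already randomised her and must analyse her.

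What follows depends on the unwritten time zero. From admission, she contributes a time that the allocation could not have affected, and the estimated difference shrinks. From catheter insertion, she has no value for the primary outcome. She becomes a post-randomisation exclusion in an open-label trial, and intent to treat in the full sense cannot be carried out. The sample size makes no allowance for either.

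**Working it through.** **1. The plan's own figures.** The stated inputs are a 4 h difference, two-sided alpha 0.05, 80% power and 71 per group. No SD is given, so the 71 cannot be reproduced independently. Solving n = 2(1.960 + 0.842)² SD² / 4² for n = 71 gives SD = 8.51 h. I use 8.5 h; this is an assumption back-solved from the plan. The inflation does reproduce: 71 / (1 − 0.20) = 88.75, so 89 per arm and 178 in total.

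**2. Admission clock.** Let f be the overall share who never receive a catheter, equal in both arms. Assume a 4 h effect in recipients and none in the others. The intent-to-treat effect is then 4(1 − f): 4.0, 3.6 and 3.2 h at f = 0, 10 and 20%. A two-sample t calculation at 89 per arm gives power of 87.7, 80.2 and 70.5%.

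The plan calls for non-parametric methods, so I take an unadjusted Wilcoxon rank-sum test by simulation. The control mean is 18 h and the recipients' mean in the 6-hour arm is 14 h. Non-recipients in both arms follow the 18 h distribution. The documents do not give the shape of the distribution, and it matters:

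| Overall non-receipt | Normal data | Right-skewed data (gamma or lognormal) |
|---|---|---|
| 0% | about 86% | about 91–95% |
| 10% | about 78% | about 84–91% |
| 20% | about 67% | about 75–82% |
| Power drops below 80% at | about 8% | about 15–20% (gamma); beyond 20% (lognormal) |

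Repeat runs move these figures by about a point. The normal model puts about 5% of 14 h-mean times below zero, so the skewed columns are at least as credible.

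**3. What this means for clinic-route women.** Only they face the gap. If they are half of the sample (assumed), 8% overall means 8 / 0.5 = 16% of them, and 15% overall means 30% of them.

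**4. Insertion clock.** Women without a catheter have no outcome. At 5, 10, 15 and 20% non-receipt, about 84, 80, 75 and 71 per arm remain. With the full 4 h effect and normal data, rank-sum power is about 85, 82, 79 and 78%. The main cost here is loss of the intent-to-treat set, not power.

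**5. Randomisation clock.** This would add the wait at home to the outcome of every clinic-route woman. As a plausibility check, suppose half come by clinic. A uniform wait of 0–48 h gives a control mean of 18 + 0.5 × 24 = 30 h. A wait of 24–168 h gives 18 + 0.5 × 96 = 66 h. Neither fits a trial planned around 18 h.

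**The case against.** **The word that places randomisation after consent gives order, not time.** Allocation could in practice be held until admission. That is possible, but nothing in the text defers it, and the plain reading is allocation in clinic. If the sponsor means admission, one sentence settles it.

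**The Specific Aims already restrict the question.** The objective is to "compare the time to delivery in women who undergo induction of labor with foley catheter and oxytocin for six vs. twelve hours", which might be taken to exclude women who never get a catheter. It states an objective, though, not an analysis set. Applied after randomisation, it would conflict with the unqualified intent-to-treat statement.

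**The effect on power may be small.** This largely stands. With right-skewed times, 80% power survives to about 15% non-receipt or beyond. A reader might infer that the trial is underpowered, but the documents do not support that, because the non-receipt rate, route mix, SD and shape are all missing. The planned adjustment for parity is not modelled here either.

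**Pre-placement events are not biasing.** This mostly stands. Labor, rupture or ripening before admission is unlikely to depend on the arm. The bias risk is limited to withdrawal or discretionary exclusion when the arm is known, and the documents do not say when it is disclosed.

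**Defining time zero would be enough.** A clock starting at admission does remove the missing-outcome problem. It leaves the dilution and any withdrawal with the arm known, and moving randomisation deals with both.

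**Conclusion.** The point holds as a design improvement that should be made. Following the plan as written puts women with no 6 versus 12 hour contrast into the primary comparison, or leaves them without an outcome, depending on the clock. It applies to the clinic route only, and a week is the typical gap, not a stated limit.

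The size is unknown. On the admission clock, 10% overall non-receipt costs roughly 4 to 8 points of rank-sum power. Whether power then drops below 80% depends on the shape of the data: it does with normal times and does not with the skewed ones. All of this rests on the back-solved SD of 8.5 h, a 4 h effect confined to recipients and an unadjusted test.

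A reader might go further and infer that waiting time at home swamps the primary outcome. The text does not exclude a clock starting at randomisation. It fits poorly, however, with the 18 h planning mean and with delivery within 12 and 24 hours as secondary outcomes, so it should not be counted as an equal alternative.

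**What to change.** Keep consent in clinic. For all three routes, re-check the existing entry criteria on labor and delivery and randomise immediately before catheter placement. Women who labor, rupture membranes, ripen or withdraw before then are never randomised. Randomisation and insertion nearly coincide, so the choice of time zero matters far less, although it should still be written down.

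The amendment is small, since two of the three routes already bring consent to labor and delivery. It has two costs. Allocation must be accessible there at all hours. More women must also be consented to randomise 178: 178/0.95 = 188, 178/0.90 = 198 or 178/0.80 = 223 (rounded up) if 5, 10 or 20% of those consented are not randomised. These rates are assumed.

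If clinic randomisation is kept, make full intent to treat the primary analysis, with a written time zero on admission that every randomised woman has, and report withdrawals before placement by arm. Any modified set should rest on objective events before admission (spontaneous labor, membrane rupture) and not on cervical-exam judgements by staff who may know the arm.

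Neither version addresses early balloon expulsion after placement, which also narrows the contrast.

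### Assigned care is the same until hour 6, so sealing each allocation until then would cheaply keep knowledge of the arm out of early care

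*Combined protocol and SAP*

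**What the plan says.** All references are to the combined protocol and SAP.

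- **Timing of randomisation (Subject Enrollment).** "Once consent is obtained, the subjects will then be randomized to either 6 vs. 12 hours with foley catheter". Consent is usually taken in clinic, and "Typically, inductions are scheduled in clinic within the week prior". Undecided women and same-day inductions are consented on labor and delivery.
- **Blinding (Subject Enrollment).** "Neither the patients nor the health care providers will be blinded to the assigned treatment group due to practical limitations". No section describes a sealed allocation or a delayed disclosure.
- **The assigned contrast (Study Procedures).** Both arms receive the same catheter, fill limit, traction and oxytocin protocol. Then: "The foley catheter will then be removed at 6 vs. 12 hours based on randomization".
- **Discretion (Study Procedures).** "health care providers may perform amniotomy at any point during the induction process", and "Labor interventions are at the discretion of the healthcare provider". The same section cites literature linking earlier amniotomy to faster delivery.
- **Expectation (Risks and Discomforts).** "we feel it is most likely that the 12-hour foley group (the current standard of care) will have longer labor inductions". As clinical experience, not as a trial procedure, the section describes active management in which "the patient is checked vaginally sooner than 12 hours and tension is applied to see if the foley is ready to come out".

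**The concern.** Removal of a catheter at hour 6 cannot be hidden, so a practical reason for openness exists from that hour. It does not cover the preceding six hours, when a woman in either arm should be treated alike and nobody at the bedside needs her arm to deliver the assigned care.

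The protocol does not say when the arm is disclosed. That it is known from consent is an inference from randomisation at consent, unblinded patients and providers, and the absence of any sealing step. If the inference is right, providers who know the arm, in a team that expects one arm to be slower, make discretionary decisions before the arms differ. Any resulting difference in care would enter time to delivery, the primary outcome, and could not be separated from the effect of catheter duration.

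A second consequence concerns interpretation. A woman whose catheter is out before hour 6 has no assigned contrast. If the overall difference is small, the natural follow-up question is what happened in women whose catheter was still in at hour 6. That comparison is like with like only if the arm could not have influenced who was still in that group, and this cannot be restored after the trial.

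**Working it through.** **1. The plan's own figures.** Inflating 71 per group for 20% cesareans gives 71 / (1 − 0.20) = 88.75, rounded up to 89, or 178 in total. This matches Biostatistical Analysis. The 71 cannot be derived directly because no SD is given. Solving for the SD that gives 80% power for 4 h at two-sided 0.05 with 71 per group yields 8.45 h by t-test (8.51 h by normal approximation). I use 8.5 h, with 9.5 h as an alternative. Both are assumptions. A t-test stands in for the planned non-parametric analysis.

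**2. False positives from a net early shift.** The standard error of the difference is SD × √(2/n) = 8.5 × √(2/89) = 1.27 h. With no true effect and a net shift b, the rejection probability is that of a two-sided t-test with noncentrality b / 1.27:

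| Net shift b (h) | SD 8.5 | SD 9.5 |
|---|---|---|
| 0 | 5.0% | 5.0% |
| 0.25 | 5.4% | – |
| 0.5 | 6.8% | 6.4% |
| 1 | 12.2% | 10.7% |
| 2 | 34.5% | 28.7% |

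For scale, a 1 h shift would need, for example, a quarter of one arm to deliver 4 h sooner (0.25 × 4 = 1).

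**3. The opposite direction.** If the shift works against a true 4 h effect, the difference to detect is 4 − b. At 89 per arm and SD 8.5, power falls from 88% to about 78, 65 or 35% for b = 0.5, 1 or 2 h.

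**4. The comparison at hour 6 if the arm is known.** Take exit time and delivery time as bivariate normal with correlation r. Retaining a share p raises the mean by r × SD × φ(c)/p, with c = z(1 − p). The ratio φ(c)/p is 0.195, 0.350 and 0.497 at p = 90, 80 and 70%. With no true effect:

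- 80% v 70% retained: 8.5 × (0.497 − 0.350) × r = 0.37 h at r = 0.3 and 0.62 h at r = 0.5.
- 90% v 70% retained: 8.5 × (0.497 − 0.195) × r = 0.77 h and 1.28 h.

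Sealing makes this spurious difference zero in expectation. Retention and correlation are assumed; the documents give neither.

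**5. Power of that comparison.** Suppose a 4 h effect exists only in women with the catheter in at hour 6, a share p of each arm. The comparison then has 89p women per arm and a 4 h difference. The all-women analysis has 89 per arm and a difference of 4p:

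| In place at hour 6 | All women, SD 8.5 | Hour-6 group, SD 8.5 | Hour-6 group, SD 9.5 |
|---|---|---|---|
| 90% | 80% | 84% | 75% |
| 80% | 71% | 80% | 70% |
| 70% | 59% | 74% | 65% |
| 50% | 35% | 59% | 50% |

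**6. Cost of missed openings.** If a share m of openings in the 6-hour arm is missed and those women lose the whole contrast, 4 h becomes 4(1 − m), that is 3.8 h at 5% and 3.6 h at 10%:

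| Setting | None missed | 5% | 10% |
|---|---|---|---|
| 89 per arm, SD 8.5 | 88% | 84% | 80% |
| 89 per arm, SD 9.5 | 80% | 76% | 71% |
| 71 per arm, SD 8.5 (cesareans excluded) | 80% | 75% | 71% |

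**The case against.** **The openness is a disclosed choice, and a 6-hour policy would be known from the start in practice.** Background and Significance looks ahead to changed induction protocols, so planning around a known removal time could be seen as part of the policy's effect. This has some force, since sealing moves the question towards catheter duration itself. But duration is what Specific Aims sets out to compare, so the objection does not defeat the change.

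**The room for early influence may be small.** Women enter with a Bishop score below 6 or dilation below 2 cm, and amniotomy is recommended only above 4 cm. The shifts in the table have no anchor in the documents, and at 0.25 h the false-positive rate is 5.4%. This stands, and it is why the figures are only illustrative.

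**Most of the open care comes later.** With a mean of 18 h, about 12 h (18 − 6) follow hour 6, including further ripening, amniotomy and cesarean decisions. This also stands. Sealing removes one route to bias, not all of them.

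**A reader might infer that many catheters are out before hour 6.** Risks and Discomforts supports only checks and adequate dilation sooner than 12 hours. It does not say before hour 6, and no section gives that share.

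**A reader might also infer that dilution makes the stated 80% power wrong.** The documents do not support this, because 4 h can be read as the meaningful difference in all women.

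**Conclusion.** The point holds as a worthwhile, low-cost improvement, not as an error or contradiction in the protocol. What the text establishes is that randomisation follows consent, patients and providers are unblinded, no sealing is described, assigned care is identical until hour 6, and care in that period is discretionary. That the arm is known from consent is inferred. Whether early care differs by arm, in which direction and by how much is unknown, so it would be wrong to conclude that the result will be biased or that it would favour the 6-hour arm.

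Under the assumed SD, the effect on the false-positive rate runs from negligible at 0.25 h to serious at 2 h. Sealing removes this route without changing the sample size or the primary population. It does not reduce dilution of the primary result or protect care after hour 6. Because the 6-hour arm already requires action at hour 6, the added risk of missed openings should be small, but it is not zero.

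**What to change.** 1. Randomise as now, and keep intent to treat in all 178 women as the primary analysis.
2. Keep each allocation sealed from the woman and her providers until hour 6 after insertion. Then open it on the labor unit with a prompt, and log the time.
3. If the catheter is already out by hour 6, the allocation may stay sealed. The woman is analysed in her assigned arm.
4. Record when each catheter came out and whether it was expelled or removed. Report the share still in place at hour 6 by arm.
5. Pre-specify, as a supportive secondary, time to delivery in women with the catheter still in at hour 6, using the same non-parametric, parity-adjusted method as the primary. State that it may have less than 80% power.

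The cost is protocol and SAP wording, two recorded times per woman, and sealed allocations available on the unit at any hour. Missed or late openings are the main downside and should be monitored through the log. Assigned removal times and provider discretion are untouched.
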